3.2.3 Evaluate the clinical status of SCA survivors 48 hours after the event

Resuscitation from SCA due to VT/VF is high in commercial use of WCD. Similar results are anticipated in hemodialysis patients. Survival will be evaluated at 48 hours after the SCA event.

3.2.4 Evaluate the incidence of potentially life-threatening arrhythmias as documented by the WCD, regardless of treatment by the WCD, at 6 calendar months

Some patients who experience VT may not lose consciousness and will use the WCD response buttons to prevent a treatment from occurring. Such patients, after the documentation of a sustained VT event, are indicated to receive an ICD. This may reduce the incidence of SCD without actual WCD therapy being delivered. Likewise, asystole may be the initial rhythm during an SCA event and impact SCA resuscitation success. Alternatively, surviving an asystole event and receiving a pacemaker may reduce SCD without defibrillation.

3.2.5 Evaluate the risk of inappropriate WCD therapy at 6 months

The rate of inappropriate therapies (i.e., a treatment shock in the absence of a VT/VF arrhythmia) during commercial WCD use is low, occurring less than 0.9% per patient-month of use. This rate will be confirmed for hemodialysis patients.

3.2.6 Evaluate compliance with WCD therapy

Compliance is high in commercial use of WCD, exceeding 90%. Similar results are anticipated in hemodialysis patients.

3.2.7 Evaluate quality of life

Psychosocial issues are one of the major concerns in the overall health of hemodialysis patients. Patients with ESRD, especially those undergoing dialysis, are under continuous stress related not only with a disease itself but also with the mode of treatment. Depression and anxiety disorders are among the most frequently encountered in ERDS patients. Social and family issues related with end-stage illness and dialysis-dependency should also be emphasized.

Quality of life will be assessed by means of a specific Kidney Disease and Quality of Life (KDQOL) survey. This questionnaire is composed of 36 questions evaluating overall health perception, kidney disease-related issues and its influence on patient's daily life as well as satisfaction with care. Kidney Disease Quality of Life Working Group website: <http://gim.med.ucla.edu/kdqol/>

3.2.8 Evaluate clinical variables that may be predictive for mortality and arrhythmic events

4. SUBJECT SELECTION CRITERIA

The population for this study will be ESRD patients who are beginning hemodialysis.

4.1 Inclusion Criteria

The specific inclusion criteria are (all must be true):

- 4.1.1 The patient has end stage renal disease requiring hemodialysis.
- 4.1.2 The patient is on hemodialysis for \leq 2 calendar months or scheduled to begin hemodialysis within 1 calendar month.
- 4.1.3 The patient is \geq 50 years of age.
- 4.1.4 The patient has a documented EF $>$ 35% within the previous calendar year.

4.1.4.1 If the patient has been hospitalized for a myocardial infarction or heart failure decompensation, the EF measurement must have occurred during the last hospitalization or after discharge.

4.2 Exclusion Criteria

The specific exclusion criteria are (none may be true):

- 4.2.1 The patient is receiving or will receive hemodialysis due to acute kidney injury and is not expected to receive subsequent chronic hemodialysis therapy.
- 4.2.2 The patient has an active ICD.
- 4.2.3 The patient has a unipolar pacemaker.
- 4.2.4 The patient has physical or mental conditions preventing him/her from interacting with or wearing a WCD. For example, patients unable to understand device use, unable to hear alarms, or unable to use response buttons.
- 4.2.5 The patient has a chest circumference at the level of the xiphoid of < 24 inches.
- 4.2.6 The patient has a chest circumference at the level of the xiphoid of > 56 inches.
- 4.2.7 The patient has an advance directive prohibiting resuscitation.
- 4.2.8 The patient has cancer or other terminal disease (excluding ESRD) with expected survival less than 6 months.
- 4.2.9 The patient is medically unstable for reasons not specifically related to kidney disease.
- 4.2.10 The patient is scheduled for live-donor kidney transplantation within 6 calendar months.
- 4.2.11 The patient is unable to consent.

5. STUDY SIZE

A minimum of 1,300 and a maximum of 2,600 subjects will be enrolled into this study. A maximum of 200 sites will enroll patients into the trial.

6. STUDY PROCEDURE

6.1 Screening

Patients undergoing hemodialysis or those with a scheduled start date for the initiation of dialysis will be screened regarding their eligibility for the study based on age, EF and length of time on hemodialysis.

6.1.1 Left ventricular ejection fraction (EF) assessment

EF must be assessed within one calendar year prior to enrollment. The most recent test must be used. In patients with a history of myocardial infarction or heart failure hospitalization within the past year, it is expected that an echocardiogram or other method for measuring EF should have been obtained during or after the time of the event. If there is more than one hospitalization for myocardial infarction or heart failure, the EF measurement used must be associated with the most recent

hospitalization. If there is no EF measurement available from the last hospitalization for myocardial infarction or heart failure, potential subjects should be treated as if no EF measurement is available.

Potential subjects who have never had an EF evaluation or whose EF was obtained greater than one calendar year prior to randomization will be required to have an echocardiogram to assess cardiac function prior to enrollment, ideally within 14 days prior to enrollment but in no circumstances later than one calendar month prior to enrollment.

Echocardiographic assessment of LVEF is most frequently performed in clinical practice. Nevertheless, similar to ICD trials, other imaging modalities (MUGA, MRI) may be used to document LVEF. Also similar to ICD trials, local assessment of LVEF will be accepted. Although there are likely to be differences in EF assessment among enrolling sites and practices, these differences are not expected to affect the outcome of the trial.

6.1.2 Patients on home hemodialysis will be eligible for enrollment in the study.

6.2 Pre-study Visit (only required if EF needs to be collected)

6.2.1 Inclusion/exclusion will be verified

6.2.2 Informed consent will be obtained.

6.2.3 Patients requiring collection of LVEF must have an echocardiogram (or other appropriate EF assessment) prior to enrollment at Visit 1. The EF assessment must be completed within 1 calendar month of the pre-study visit but ideally should be completed within 14 days.

6.2.4 Enrollment will occur once all screening criteria have been met, including EF.

6.3 Visit 1 (Day 1)

Prior to Visit 1, call ZOLL to schedule a Patient Service Representative (PSR) to be present the day of enrollment. A PSR should be available to fit the patient with a WCD in the event that the patient is randomized to the WCD arm.

For all subjects:

6.3.1 Inclusion/exclusion will be verified.

6.3.2 Informed Consent will be obtained.

6.3.3 Subjects will be randomized to WCD or conventional therapy.

6.3.4 Clinical history data will be collected, including laboratory and ECG if available.

6.3.5 Subjects will be asked to complete quality of life questionnaire.

6.3.6 If the patient has started hemodialysis, general hemodialysis data will be collected.

6.3.7 Medication usage will be collected.

For subjects randomized to WCD only:

6.3.8 Subjects will be instructed and trained regarding usage of WCD by a ZOLL representative.

6.3.9 Subjects will be instructed to wear the WCD for six months.

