7.2 Statistical Methods

The primary analysis will be based on a 1-df likelihood ratio test (LRT) of the null hypothesis that the 6 calendar month SCD mortality rate is identical for subjects randomized to WCD versus non-WCD (i.e. odds ratio of 1), conditional on enrolling site and date of enrollment (stratification variables that define randomized blocks), and further

parametrically adjusted for five additional pre-specified risk factors via conditional logistic regression (CLR):

- age (continuous, and flexibly modeled via a 4-df continuous piecewise linear spline with knots at 60, 70, and 80 years of age, allowing for a separate odds ratio per year within each decade of age),
- ejection fraction (continuous, and modeled via a 2-df continuous piecewise linear spline with a knot at 50%, allowing for a separate odds ratio per year above and below 50%, given that it is expected that mortality risk likely decreases smoothly up to about 50% but then perhaps levels off thereafter),
- race/ethnicity (binary: white non-Hispanics versus all others),
- diabetes (binary: yes versus no),
- myocardial infarction (binary: yes versus none),
- dialysis access (binary: catheter versus no catheter).

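### Section 6.3 lists randomisation before the baseline KDQOL, and nothing in the protocol requires that questionnaire before the subject knows the arm

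*Combined protocol and SAP*

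**What the plan says.** Section 6.3 (Visit 1, Day 1) numbers the steps for all subjects. Eligibility (6.3.1) and consent (6.3.2) come first. Then:

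- randomisation, at 6.3.3: "Subjects will be randomized to WCD or conventional therapy"
- the history, with any laboratory results and ECG that exist (6.3.4)
- the baseline KDQOL, at 6.3.5: "Subjects will be asked to complete quality of life questionnaire"
- dialysis data, for those who have already started haemodialysis (6.3.6)
- current medication (6.3.7)

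Training of WCD subjects comes after this, at 6.3.8. The opening of 6.3 asks the site to arrange for a sponsor representative to be there on the day, so that a subject drawn to the WCD arm can be fitted.

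The pre-study visit (6.2) is only for patients who need an EF measurement, and it covers eligibility, consent and EF. Table 3 puts every Visit 1 item in a single column. Quality of life, measured by KDQOL, is secondary objective 3.2.7. The primary model in Section 7.2 adjusts for age, EF, race/ethnicity, diabetes, myocardial infarction and dialysis access.

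**The concern.** KDQOL is answered by the subject, and Section 3.2.7 describes it as covering perceived health, the effect of kidney disease on daily life, and satisfaction with care. A subject who has just been told to wear a defibrillator vest for six months, or has just been told there will be no vest, may answer differently from one who does not yet know. A baseline taken at that point is no longer a pre-treatment measurement, and it cannot be retaken later. Any quality-of-life comparison that uses it would carry the difference forward.

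A lesser worry is that history and dialysis data are also listed after randomisation, and some of the covariates in the primary model would come from them.

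**Working it through.** No figure in the plan bears on this point, so the check is mainly of the text.

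**1. Position relative to randomisation, in the two places that could fix it.**

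| Item | Section 6.3 | Table 3 row |
|---|---|---|
| Medical history | after (6.3.4) | above Randomization |
| Laboratory | after (6.3.4) | above Randomization |
| KDQOL | after (6.3.5) | below, last row |
| Dialysis data, medication | after (6.3.6, 6.3.7) | below |
| WCD training | after (6.3.8, WCD subjects only) | above Randomization |

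Table 3 reverses 6.3 for history and laboratory. It also places WCD training above Randomization, although 6.3.8 gives training only to subjects already randomised to WCD. Its row order is therefore not a reliable sequence. For KDQOL, neither place puts the questionnaire before randomisation, and the Table 3 footnotes say nothing on timing relative to it.

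**2. Is there an earlier baseline?** No. Section 6.2 collects neither KDQOL nor history, and many subjects will not need that visit.

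**3. Does the subject know the arm?** Yes, in effect. The comparator is conventional therapy without a sham, and fitting is planned for the same day. Section 6.10.3 blinds clinicians to arrhythmia recordings, and Section 7.1 blinds the Mortality Committee. Neither hides the assignment from the subject or the site at Visit 1.

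**4. Is the baseline answer tied to the time before assignment?** Not by the protocol text. The KDQOL items at Visits 2 and 4 state a recall period (6.4.1.1, 6.6.1.4); the item at Visit 1 states none.

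**5. Possible size for quality of life (assumptions, not document figures).** Let b be the shift in the WCD arm's baseline mean, relative to control, caused by knowing the arm, in SD units. Let follow-up be unaffected, and let s be the within-arm slope of follow-up on baseline.

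- Change from baseline: bias = −b. For b = 0.05 to 0.20, this is −0.05 to −0.20 SD.
- Baseline-adjusted: bias = −s × b. For s = 0.3 to 0.7, this runs from −0.3 × 0.05 = −0.015 SD to −0.7 × 0.20 = −0.14 SD.
- Follow-up scores only: no bias by this route.

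The sign reverses if b is negative. Section 7 does not say which of these analyses, if any, will be used.

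**6. Covariates of the primary model.** Age cannot be affected. EF is obtained before enrolment (6.1.1). A recent hospitalisation for myocardial infarction must already be known to judge whether the EF is valid (4.1.4.1, 6.1.1). Diabetes, infarction and catheter access enter as yes/no facts that are normally in the record. The text does not say on which form diabetes or access is captured.

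**The case against.** The strongest reply is that a numbered list is not a work instruction. No section says the items of 6.3 must be done in that order, and the document's lists are not consistently chronological: 6.3 puts eligibility before consent, while Table 3 puts consent first. The case report form instructions, which might settle the order, are not part of these documents. This stands. A reader might infer that both baselines are in fact taken after the arm is known, but the documents show only that they may be.

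It can also be said that the bias falls on an analysis nobody has planned. Section 3.2.7 names the instrument and stops there. This stands too, so a statement that any reaction to assignment passes in full into a reported treatment effect is not supported. It does not remove the point, because a baseline KDQOL is collected and nothing excludes its use.

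A reader might go further and conclude that the primary analysis is compromised, because Section 7.2 relies on treatment being independent of the risk factors. That does not follow. The statement there supports the claim that adjustment costs little efficiency. It concerns the risk factors themselves, not the order in which they are recorded. Differential recording of coarse, documented facts on the day of assignment is possible in principle, but nothing in the documents suggests that it would be material.

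**Conclusion.** The point holds as a gap in the procedure. Section 6.3 lists the KDQOL baseline after randomisation, no section requires it earlier, and Table 3 does not repair this. A site following 6.3 in order would take a self-reported baseline from a subject who knows the arm, and that would bias any analysis for objective 3.2.7 that uses baseline. The size cannot be derived from the documents; the ranges in the working depend wholly on the assumed shift and slope.

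The effect on the primary-model covariates is secondary and small. Ascertainment of death is not affected, and neither are the stated power, alpha and sample size.

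**What to change.** Reorder 6.3 so that KDQOL, clinical history with laboratory and ECG, dialysis data and medication are completed before randomisation is released, with WCD fitting and training after it. State in one sentence that this order is required. Rearrange the rows of Table 3 to match, or add a footnote that the baseline items precede disclosure of the arm.

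This is a free improvement: the same items are collected at the same visit, with no added burden on the subject. If sites are already enrolling, an instruction to sites and a recorded time of KDQOL completion relative to randomisation would show which baselines were taken beforehand.

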6.4 Visit 2 (2 calendar months from enrollment \pm 14 days)

6.4.1 For all subjects:

6.4.1.1 Subjects will be asked to complete quality of life questionnaire reflecting their experience over the previous 4 weeks.

6.4.1.2 Collect general hemodialysis data.

6.4.1.3 Collect any changes to medications.

6.4.1.4 Collect device, adverse, and cardiac event information including laboratory data from the medical record as available.

6.4.2 For subjects randomized to WCD therapy:

6.4.2.1 Compliance will be evaluated and encouraged.

6.5 Visit 3 (4 calendar months from enrollment \pm 14 days)

6.5.1 For all subjects:

6.5.1.1 Collect general hemodialysis data.

6.5.1.2 Collect any changes to medications.

6.5.1.3 Collect device, adverse and cardiac event information including laboratory data from the medical record as available.

6.5.2 For patients randomized to WCD therapy:

6.5.2.1 Compliance will be evaluated and encouraged.

6.6 Visit 4 (at least 6 calendar months from enrollment, with up to 14 additional days)

6.6.1 For all subjects:

6.6.1.1 Collect general hemodialysis data.

6.6.1.2 Collect any changes to medications.

6.6.1.3 Collect device, adverse and cardiac event information as needed.

6.6.1.4 Subjects will be asked to complete quality of life questionnaire reflecting their experience over the past calendar month.

6.6.2 Collect survival data.

6.7 Unscheduled Visit (e.g., if resuscitation from SCA)

6.7.1 For all subjects:

6.7.1.1 Collect general hemodialysis data.

6.7.1.2 Collect any changes to medications.

6.7.1.3 Collect device, adverse and cardiac event information as needed, including laboratory data as available from medical record.

6.7.2 For patients randomized to WCD therapy:

6.7.2.1 Compliance will be evaluated and encouraged.

6.8 Final survival assessment (1 calendar year from enrollment, with up to 14 additional days)

Sites will be asked to determine survival for all subjects enrolled in the study through either routine dialysis records and appointments, or a phone call to the subject.

6.9 Post-study follow-up

Long-term outcome assessment may be performed using databases maintained by the United States Renal Data System and the Centers for Medicare and Medicaid.

Table 3: Visit and Data Collection Schedule

	Pre-study Visit ^a	Visit 1 (Enrollment)	Visit 2 (Month 2)	Visit 3 (Month 4)	Visit 4 (Month 6) or Terminal Event or Withdrawal	Unscheduled Visit or SCA Event
Consent	X	X				
Confirm Inc/Exc (confirm presence of EF or schedule echocardiogram)	X ^b	X				
Medical History/ESRD History		X ^c				
Laboratory Assessment ^e		X	X ^f	X ^f	X ^f	X
WCD Introduction/Training		X				
Randomization		X				
WCD Fitting (WCD subjects only)		X ^d				
WCD Compliance (for WCD subjects only)		X ^d	X ^d	X ^d	X ^d	X ^d
Collection of Dialysis Information and Medication Use		X	X	X	X	X
Collect device, adverse and cardiac events (includes defibrillation events)			X	X	X	X
KDQOL (Quality of Life)		X	X		X ^g	

^a for patients without EF data

^b LVEF must have been collected within 1 calendar year prior to enrollment, or during or after MI or CHF hospitalization, whichever is more recent. LVEF may be collected from Echocardiogram, MUGA, MRI.

^c included ECG if available

^d for WCD subjects only

^e collected at local lab

^f only if cardiac event/shock occurs

^g if not terminal event

6.10 Managing WCD Therapy

6.10.1 The WCD System continuously monitors and records critical patient data to help diagnose and treat arrhythmic conditions. Device data will be uploaded at least weekly to a central server located in Pittsburgh, PA. In the event that uploads are not occurring on a routine basis, subjects should call ZOLL Technical Support for instructions.

6.10.2 Subjects having questions or difficulty managing their WCD should be instructed to call ZOLL Technical Support.

6.10.3 Clinicians will be blinded to the arrhythmia recordings in the group assigned to wear the WCD. This is necessary to prevent co-interventions with inappropriate anti-

arrhythmic drugs or early implantation of an ICD. If unblinding is required, the investigator may be able to view the device recorded data through a secure website and/or receive ECG strips recorded by the WCD. The following provisions for unblinding are available when clinically indicated.

- 6.10.3.1 Automatic unblinding will be initiated by ZOLL, and results in electronic notification to the site as well as the transmission of ECG data. Automatic unblinding will be initiated when any of the following events occurs:
 - 6.10.3.1.1 The subject receives a treatment by the WCD.
 - 6.10.3.1.2 VT/VF lasting \geq 30 seconds is detected and recorded by the WCD, regardless of treatment by the device.
 - 6.10.3.1.3 Asystole or bradycardia less than 20 BPM is detected and recorded by the WCD.
- 6.10.3.2 Clinical sites can request unblinding and receive ECG strips recorded by the WCD under the following circumstances:
 - 6.10.3.2.1 Subject suffers a cardiac arrest or reports receiving a shock.
 - 6.10.3.2.2 Subject complains of excessive alarms or alarms suspicious of an arrhythmic event that is not associated with syncope, pre-syncope or palpitations. In this circumstance, a protocol deviation will be reported.
 - 6.10.3.2.3 Subject complains of syncope or pre-syncope associated with WCD alarms.
 - 6.10.3.2.4 Subject complains of palpitations associated with WCD alarms.
 - 6.10.3.2.5 A treating physician deems it to be medically necessary. In this circumstance, a protocol deviation will be reported.

7. STUDY DESIGN

This study will employ a group sequential two-arm randomized clinical trial to test the hypothesis that the wearable cardioverter defibrillator (WCD) reduces overall mortality within a 6 calendar month period beginning at the time of randomization, which is to occur no later than 2 calendar months after the initiation of hemodialysis.

Enrolled subjects will be 1:1 randomized to WCD or non-WCD, stratified by enrolling site and, implicitly, by calendar time of enrollment. All subjects will be followed for at least 6 calendar months regardless of compliance. The primary endpoint is the binary event of whether or not sudden cardiac death occurs within the 6 month follow-up period. The primary analysis will be an intention-to-treat analysis based on the randomization, ignoring the fact that some subjects randomized to WCD may discontinue use of the device early while some subjects randomized to the non-WCD arm may obtain and wear a WCD.

Overall mortality at 6 calendar months in the non-WCD arm is expected to be 14%, with one quarter of all deaths due to sudden cardiac death (SCD rate of 3.5%).² Taking some anticipated noncompliance into consideration, as some subjects are expected to discontinue WCD prior to 6 months, we hypothesize that the WCD will provide a relative reduction in SCD of 60%. Thus, we

expect an absolute reduction of 2.1% in SCD mortality, corresponding to a relative risk (RR) of 0.40 and an odds ratio (OR) of 0.39.

The exact number of subjects to be randomized is uncertain since the group sequential trial was designed to have 46% power to stop at the first interim look at 650 (50%) subjects per arm, and 69% power to stop at the second interim look at 975 (75%) subjects per arm, while controlling the overall significance level at $\alpha = 0.05$. But if the study continues to the third and final look, a maximum of 1,300 subjects will be enrolled in each arm, for a total of 2,600 subjects providing 91% power to detect the hypothesized 60% relative reduction in overall 6-month SCD mortality from 3.5% down to 1.4%.

7.1 Endpoint Assessment

A Mortality Committee will provide an assessment regarding mortality events with a categorization of the death based on underlying cause and mechanism of death. All deaths will be adjudicated by the Mortality Committee and classified as 'sudden (SCD)', 'not sudden' or 'indeterminate'. In addition, the death will be classified as 'cardiac', and 'non-cardiac'. All deaths will be used as endpoints in the primary analysis and the adjudicated results used as endpoints in the secondary analyses.

This committee will be blinded to information regarding the use of a WCD. The death reports from enrolling sites will be transcribed by an unblinded individual and provided in a uniform format to the adjudication committee. Transcribed notes will be redacted of information regarding WCD or WCD therapy to maintain the blinding of the committee. The Mortality Committee will not utilize WCD or AED interrogation information when classifying death as cardiac or non-cardiac, and as sudden or non-sudden.

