4D ⁶	Atorvastatin RCT in HD+ DM (type II) pts, composite endpoint of cardiac death, nonfatal MI, stroke. (1998-2002)	n=1255 (control group=636, treatment group=619) European HD patients	46.1	65.7 ± 8.3	100	>43	NR	25.9	59.2	Unexpected death without $K^+ > 7.5$ mmol per liter before the start of the three most recent sessions of HD (sudden cardiac death)
HEMO ^{7,8}	RCT of high-flux dialyzer membrane on survival or morbidity with cardiac event sub-analysis. (1995-2000)	n=1846 HD patients	56.2	57.6 ± 14.0	44.6	80.1 (pre-existing CD)	NR	24.9	23.9	Witnessed or unwitnessed unexpected death; symptoms onset < 24 hours if witnessed or < time since last dialysis session if unwitnessed.
DOPPS (US) ²⁰	Prospective, observational study of HD patients in EU, Japan, and US (1996-2002)	n=3856 US HD pts (Total study N=16,720)	46.6	60.5 ± 15.5	45.7	83.2(HTN)	NR	NA	NR	NA
Bleyer ¹⁸	Retrospective examining sudden death in HD patients.	n=80 sudden deaths (total N=228)	58.8	60.3 ± 14.1	57.5	92.5 (HTN) 56.3 (CAD)	75.3 (EF >35%)	35	80	Cardiovascular related (73% of SD due to SCA)
EVOLVE ⁴⁴	Prospective study of cinacalcet	3883 hemodialysis patients	40	55.4	33.4%	NR	NR	24.5	45	NR
Mangrum ^{21,22}	Single-center, retrospective mortality analysis of prevalent hemodialysis pts evaluating SCD and LV function (1999-2003)	N= 241 HD patients		NR	NR	NR	63.0 (89 pts echo available)	35	74	Arrhythmias/SCA
Pun (2009) ²³	Retrospective study of GFR and risk of SCD in a CKD cohort. Duke Databank for Cardiovascular Disease (DDCD) was used. (1995-2006)	n=424 HD (58.7%) and non-HD pts (eGFR<15 ml/min) with documented CAD	48.6	61 (median)	63.0	89.4 (HTN)	52 (IQR 40, 60)	24.2 per 1000 patient years (HD pts)	NR	Death resulting from the sudden, unexpected cessation of cardiac activity with hemodynamic collapse

*Out of total mortality

[figure not shown]

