7.1.1 SCD definitions

For witnessed deaths, sudden cardiac death (SCD) will be defined as an unexpected, non-traumatic, non-self-inflicted fatality in otherwise stable subjects who die within one hour of the onset of the terminal symptoms (and for whom dialysis-noncompliance or withdrawal have been excluded). Subjects dying more than one hour after a sudden cardiac arrest (SCA) from a ventricular arrhythmia will be designated as non-sudden death due to ventricular arrhythmia.

For unwitnessed deaths, participants will meet the definition of sudden cardiac death if they are found dead within 24 hours of being well, assuming there is no evidence of another cause of death during that time period including dialysis-noncompliance (or withdrawal). Autopsy results may be used when available.

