7.3 Group Sequential Design

Standard group sequential methods³⁸ can be applied, given the large-sample approximate normality of the estimated log(OR), and PASS 11 software was used to compute the alpha and power values for our custom group sequential stopping rule. We plan to conduct 2

interim analyses once the 6 calendar month SCD outcome has been observed for 1/2 and 3/4 of the subjects. Our custom stopping boundaries retain 4% nominal alpha for the third and final look, provided the study doesn't stop early, while testing each of the 2 interim analyses at the nominal alpha level of 0.01375 (see Table 4). The overall alpha level for the study is .05.

Table 4: Group sequential design for the two-arm randomized clinical trial.

Look	Relative Information	# WCD subjects	# non-WCD subjects	# Total subjects	Nominal Alpha	Corrected Alpha
1	50%	650	650	1,300	0.01375	0.01375
2	75%	975	975	1,950	0.01375	0.02231
3	100%	1,300	1,300	2,600	0.04000	0.05000

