7.6 Statistical Analysis

Upon completion of the trial, a two-tailed p-value will be computed as the probability of the realized stopping point (under null conditions) plus the probability of all more extreme stopping points, defined via the stagewise ordering of the sample space.³⁸ If the study stops at the first look, $p \leq 0.01375$ and inference proceeds as if there were no future potential stopping rules. If the study stops at the second look, we know $0.01375 < p \leq 0.02231$; and if the study continues to the third and final look, then either $0.02231 < p \leq 0.05$ (if nominal $p \leq 0.04$) or else $p > 0.05$ (if nominal $p > 0.04$). SAS PROC SEQTEST will be used to compute the actual p-value, as well as a median unbiased estimated OR, along with 95% confidence intervals (CI).

A point estimate of the true OR, a *median unbiased estimate*, is that value for OR for which the probability of stopping points more extreme than the reached stopping point equals the probability of stopping points less extreme than the reached point — and hence the estimate is just as likely to underestimate as to overestimate the true risk ratio. Confidence bounds for the OR are found similarly: the value of OR for which the probability of more extreme values is at most 2.5% and the value of OR for which the probability of less extreme values is at most 2.5% together yield a 95% confidence interval for OR.

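### The plan lets a death be adjudicated 'indeterminate' but does not say how such a death counts in the yes/no SCD primary endpoint, and it contradicts itself on which deaths are primary events

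*Combined protocol and SAP*

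**What the plan says.** - **Endpoint.** Section 7: "The primary endpoint is the binary event of whether or not sudden cardiac death occurs within the 6 month follow-up period". Section 7.2 applies a 1-df likelihood ratio test (LRT) to the 6-month SCD rate, and the power tables in Sections 7.3 and 7.4 are built on SCD.
- **Adjudication.** Section 7.1: "All deaths will be adjudicated by the Mortality Committee and classified as 'sudden (SCD)', 'not sudden' or 'indeterminate". Only the first of the three labels is SCD.
- **Conflicting sentence.** Later in the same paragraph, Section 7.1 assigns all deaths to the primary analysis and the adjudicated categories to the secondary analyses. The opening of Section 7 also gives overall mortality as the hypothesis. Section 7.2, by contrast, makes all-cause mortality an exploratory secondary endpoint.
- **Unwitnessed deaths.** Section 7.1.1 counts these as SCD if "they are found dead within 24 hours of being well", provided no other cause is evident, dialysis non-compliance included. It gives no rule for a body found later. The HEMO row of Table 1 shows another window: "< time since last dialysis session if unwitnessed".
- **Safeguards.** Section 7.1 blinds the committee to WCD use, supplies site reports transcribed to a uniform format with WCD content removed, and bars WCD and AED interrogation data from the classification.

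Nothing maps 'indeterminate' to yes or no. Section 13 has the DSMB validate the events used for the stopping rule but adds no mapping.

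**The concern.** A three-way label feeding a two-way endpoint needs a rule. Without one, the analyst must choose a coding, possibly after seeing the data. If indeterminate deaths are coded as non-events, they are analysed like survivors. Should SCDs in one arm be harder to classify, that arm's SCD count falls although nobody has been saved, and the primary test reads the fall as an effect.

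The category may well be used. Section 1.1 says most SCD happens outside dialysis centres and is very unlikely to be witnessed, and Section 1.2.1 reports a 3-fold risk at the end of the dialysis-free weekend. A subject found more than 24 hours after last being seen well falls outside the unwitnessed rule.

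The arms could also differ in the information that reaches the committee. Assignment is open, and the redacted WCD content would arise mainly in one arm. Under Section 6.10.3.1, sites receive ECG data after a WCD treatment, after VT/VF of at least 30 seconds, or after asystole or severe bradycardia. Removing such detail may remove evidence on timing.

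**Working it through.** **1. Inputs from the plan.** Two-sided design: "The overall alpha level for the study is .05" (Section 7.3) and "a two-tailed p-value will be computed as the probability of the realized stopping point" (Section 7.6). Looks at 650, 975 and 1,300 per arm, with "testing each of the 2 interim analyses at the nominal alpha level of 0.01375" and 0.04 at the end ("Our custom stopping boundaries retain 4% nominal alpha for the third and final look"). Control SCD 3.5%, WCD 1.4%, control all-cause mortality 14% (Section 7).

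**2. The plan's own figures reproduce.** Three-look multivariate normal integration at information 0.5, 0.75 and 1 gives cumulative alpha 0.0137, 0.0223 and 0.0500, against 0.01375, 0.02231 and 0.05000 in Table 4. For power, the continuity-corrected drift is

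(p1 − p2 − 1/n) / √(2p̄(1 − p̄)/n) = (0.035 − 0.014 − 1/1300) / √(2 × 0.0245 × 0.9755/1300) = 3.336,

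which gives 45.8%, 69.1% and 90.6%, against the stated 46%, 69% and 91%. All nine rows of Table 5 match after rounding.

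**3. Expected counts at full size.** Control: 1,300 × 14% = 182 deaths, of which 1,300 × 3.5% = 45.5 are SCD. WCD: 1,300 × (14% − 2.1%) = 154.7 deaths, of which 1,300 × 1.4% = 18.2 are SCD. That is about 64 primary events in total.

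**4. One-arm loss with no true effect.** True SCD is 3.5% in both arms. A share d of WCD-arm SCDs is labelled indeterminate and coded as non-event, so the observed WCD rate is 3.5% × (1 − d). The planned looks were simulated with an unadjusted LRT on binomial counts (200,000 to 400,000 runs). The documents give no indeterminate rate, so every d is an assumption.

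| d (WCD arm only) | Chance of a significant result favouring WCD |
|---|---|
| 0 | about 2.5% |
| 5% | about 4% |
| 10% | about 7% |
| 20% | about 17% |
| 30% | about 34% |
| 40% | about 57% |

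The set-up is symmetric, so the same loss in the control arm alone gives the same chances of a result against the device.

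**5. The same thing in deaths.** With 46 control SCDs at the final look, the LRT needs 28 or fewer in the WCD arm. At 46 against 28 the statistic is 2[46 ln(46/37) + 28 ln(28/37) + 1254 ln(1254/1263) + 1272 ln(1272/1263)] ≈ 4.55, so p ≈ 0.033, below 0.04. From 46 expected, that is a net loss of 18 deaths (18/46 = 39%), or about 10% of the 182 deaths in an arm. At the second look it takes 18 of 34, and at the first 14 of 23.

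**6. Equal loss in both arms.** No false positive arises, but power at RR 0.40 on the LRT scale falls from 93.8% to 91.3% (10% lost) or 87.8% (20% lost). The LRT without continuity correction starts above the plan's 91%.

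**7. All-cause mortality as a check.** For 14% against 11.9% at two-sided 0.05: z = 0.021 / √((0.14 × 0.86 + 0.119 × 0.881)/1300) = 1.595, and Φ(1.595 − 1.96) ≈ 36% power.

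**8. Counting indeterminate deaths as SCD in both arms.** Non-sudden mortality is 14% − 3.5% = 10.5% in control and 11.9% − 1.4% = 10.5% in WCD. If a share q of these deaths is also indeterminate, equally in both arms (assumed), each rate rises by 10.5% × q.

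| q | Control vs WCD rate | Observed RR | Power (LRT scale) |
|---|---|---|---|
| 0 | 3.5% vs 1.4% | 0.40 | about 94% |
| 5% | 4.025% vs 1.925% | 0.48 | about 88% |
| 10% | 4.55% vs 2.45% | 0.54 | about 82% |
| 20% | 5.6% vs 3.5% | 0.63 | about 72% |

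Two-sided alpha stays at about 5.1% at q = 5% and 10%.

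The simulations omit site and date conditioning and the covariates of Section 7.2.

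**The case against.** The strongest reply is that non-event coding appears nowhere in the plan. That is right. A reader might infer from Sections 7 and 7.2 that indeterminate deaths enter as non-events, but this is only the natural default, and the all-deaths sentence in Section 7.1 points the other way. That sentence does not settle the matter either, because it contradicts the endpoint, the test and the power section. What stands is a missing rule plus a contradiction.

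The safeguards are real. A blinded committee, uniform redacted reports and an unwitnessed rule that defaults to SCD within 24 hours all narrow the room for an arm difference. Blinding equalises judgement, however, and not the information supplied.

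A reader might also infer that the bias would favour the device. Nothing in the documents fixes the direction, and loss in the control arm would work against it. Nor do they show how large the category will be. Some deaths after missed dialysis may be called not sudden under Section 7.1.1. Table 1 gives the HEMO definition without a reason, so it shows an alternative window and no more. Most expected deaths are non-sudden, and under non-event coding, labelling those indeterminate leaves the SCD count unchanged.

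Finally, all-cause mortality is immune to classification and is analysed by the same method. That is a genuine check, but an exploratory one with about 36% power.

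**Conclusion.** The point holds in this form: the plan does not say how indeterminate deaths enter the primary endpoint, contradicts itself on which deaths are primary events, and has no sensitivity analysis for the choice. If they are coded as non-events, unequal classifiability alone can shift the primary result. A 10% one-arm loss of SCDs nearly triples the favourable false-positive rate, from about 2.5% to 7%. A 5% loss moves it only to about 4%, and a false positive becomes more likely than not only near 40%.

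These sizes rest on assumed loss rates, loss confined to one arm, no true effect and an unadjusted LRT. They show how sensitive the test is and do not predict what will happen. The documents do not support saying that the trial is biased towards the WCD. They do support settling the rule before any outcome is compared by arm, because the same coding drives the interim stopping decisions.

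**What to change.** Before the first interim look:

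1. Reconcile the all-deaths sentence in Section 7.1, and the overall-mortality hypothesis that opens Section 7, with the SCD endpoint in Sections 7 and 7.2.
2. State in Sections 7.1 and 7.2 how an indeterminate death is coded in the primary analysis. Say also which label applies to an unwitnessed death found more than 24 hours after the subject was last well with no other cause evident.
3. Pre-specify a supportive analysis using the same LRT with indeterminate deaths counted as SCD in both arms.
4. Report indeterminate counts by arm at each look (to the DSMB) and at the end.
5. Interpret the supportive analysis by the direction and size of its odds ratio, and not as a second significance hurdle.

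The cost is protocol wording and one extra model run on the committee's existing labels. The supportive estimate is diluted by non-arrhythmic deaths: its power falls from about 94% to 88%, 82% or 72% if 5%, 10% or 20% of non-sudden deaths are also indeterminate (assumed). This is why it should not act as a gate.
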